 - 10.3.1. Safety Analyses 34
 - 10.3.1.1. Clinical Evaluation of Safety 34
 - 10.3.1.2. Statistical Evaluation of Safety 35
 - 10.3.2. Pharmacokinetic Analyses 35
 - 10.3.2.1. Pharmacokinetic Parameter Estimation 35
 - 10.3.2.2. Pharmacokinetic Statistical Inference 35
 - 10.3.3. Evaluation of Immunogenicity 36
 - 10.3.4. Interim Analyses 36
- 11. References 37

List of Tables

| Table | | Page |
|---------------|--------------------------------|-------------|
| Table GBGM.1. | Objectives and Endpoints | 14 |
| Table GBGM.2. | Treatments Administered..... | 22 |
| Table GBGM.3. | Treatment Sequences | 23 |

List of Appendices

| Appendix | | Page |
|-----------------|---|-------------|
| Appendix 1. | Abbreviations and Definitions | 38 |
| Appendix 2. | Clinical Laboratory Tests..... | 41 |
| Appendix 3. | Study Governance, Regulatory and Ethical Considerations | 42 |
| Appendix 4. | Hepatic Monitoring Tests for Treatment-Emergent Abnormality | 45 |
| Appendix 5. | Blood Sampling Summary | 46 |
| Appendix 6. | Pancreatic Monitoring | 47 |

1. Protocol Synopsis

Title of Study:

Relative Bioavailability of an Investigational Single Dose of Dulaglutide after Subcutaneous Administration by a Single Dose Pen Compared to a Prefilled Syringe in Healthy Subjects

Rationale: The current commercially used single dose pen (SDP) at the same injection volume (0.5 mL) and a new higher dulaglutide concentration formulation will be used for dose delivery in future Phase 3 studies evaluating investigational dulaglutide doses that are higher than the currently approved 0.75- and 1.5-mg doses.

Study GBGM will evaluate the relative bioavailability of a 4.5-mg dulaglutide dose administered subcutaneously (SC) as a single SDP injection of the higher dulaglutide concentration (test) compared to the same dose administered as three 1.5-mg prefilled syringe (PFS) injections of the current commercial formulation (reference).

Objectives/Endpoints:

| Objectives | Endpoints |
|---|--|
| 
Primary To evaluate the relative bioavailability of a single dose of dulaglutide administered SC to healthy subjects as a single injection by SDP (test) compared to 3 injections by PFS (reference).
 | Pharmacokinetic parameters including area under the concentration versus time curve (AUC) and maximum observed drug concentration (C_{max}) for dulaglutide administered by a SDP compared to PFS. |
| 
Secondary To assess the tolerability of a single dose of dulaglutide administered SC to healthy subjects as a single injection by SDP compared to 3 injections by PFS.
 | Incidence of treatment-emergent adverse events (AEs). |

Summary of Study Design:

Study H9X-MC-GBGM is a Phase 1, single-center, open-label, randomized, 2-period, crossover study in healthy subjects to evaluate the relative bioavailability of 4.5 mg dulaglutide administered SC as a single injection by SDP (test) compared to 3 injections by PFS (reference).

Treatment Arms and Planned Duration for an Individual Subject:

Subjects will undergo a screening examination within 27 days prior to enrollment. For Periods 1 and 2, on the morning of Day 1 of each period, subjects will receive a single SC dose of dulaglutide administered according to their assigned treatment sequence following an overnight fast of approximately 8 hours. At a minimum, subjects will remain at the clinical research unit (CRU) until collection of the 168-hour (Day 8) pharmacokinetic (PK) sample. There will be a washout period of at least 28 days between doses in Periods 1 and 2. Each subject will be required to return to the CRU for a follow-up visit 28±3 days after the last dulaglutide dose. The total duration for each subject (from screening through the follow-up visit) is approximately 84 days.

Number of Subjects:

Approximately 24 subjects will be enrolled in order that at least 18 subjects complete the study.

Statistical Analysis:

Pharmacokinetic: The primary PK parameters to be estimated for dulaglutide will be C_{\max} and AUC from time zero to infinity (AUC[0- ∞]). Other noncompartmental parameters, such as AUC from time zero to 168 hours (AUC[0-168h]), AUC from time zero to 336 hours (AUC[0-336h]), time to C_{\max} (t_{\max}), apparent terminal elimination half-life, apparent total body clearance of drug, apparent volume of distribution, and AUC from time zero to time t, where t is the last time point with a measurable concentration (AUC[0- t_{last}]), may be reported.

The PK parameter estimates will be evaluated to determine the relative bioavailability of dulaglutide administered SC by SDP (test) compared to dulaglutide administered by PFS (reference). The PK parameters will be summarized using descriptive statistics by treatment. Log-transformed C_{\max} and AUC(0- ∞) (primary parameters) and AUC(0-168h) and AUC(0-336h) (secondary parameters) will be evaluated in a linear mixed-effects analysis of variance model with fixed effects for treatment (SDP or PFS), period, and sequence and a random effect for subject within sequence. The ratios of least squares geometric means of SDP compared to PFS, as well as the corresponding 90% confidence intervals (CIs), will be estimated and reported. The t_{\max} will be analyzed nonparametrically using the Wilcoxon ranked sum test. Estimates of the median difference and the corresponding 90% CIs will be calculated. Additional analysis may be conducted if deemed appropriate.

Safety: All investigational product and protocol procedure AEs will be listed, and if the frequency of events allows, safety data will be summarized using descriptive methodology. The incidence of symptoms for each treatment will be presented by severity and by association with investigational product as perceived by the investigator. Symptoms reported to occur prior to enrollment will be distinguished from those reported as new or increased in severity during the study. Each symptom will be classified by the most suitable term from the medical regulatory dictionary. The number of investigational product-related serious AEs will be reported. Safety parameters that will be assessed include safety clinical laboratory parameters and vital signs. The parameters will be listed and summarized using standard descriptive statistics. The change from baseline (Day 1 predose of each period) in vital signs will be analyzed and summarized. The change from baseline (Day -1 of each period) in amylase and lipase will also be summarized. Electrocardiograms and physical examinations will be performed for safety monitoring purposes and will not be presented. Additional analysis will be performed if warranted upon review of the data.

2. Schedule of Activities

Study Schedule Protocol H9X-MC-GBGM

| Procedure | Screening | Periods 1 and 2 | | | | | | | | | | ET/Follow-up | Comments | |
|--|----------------|-----------------|-------------------|-------|-------|-------|-------|-------|-------|-------|--------|--|----------|--|
| | Days -28 to -2 | Day -1 | Day 1 | Day 2 | Day 3 | Day 4 | Day 5 | Day 6 | Day 7 | Day 8 | Day 15 | 28 ±3 days after last dulaglutide dose | | |
| Informed Consent | X | | | | | | | | | | | | | |
| Subject Admission to CRU | | X | | | | | | | | | | | | |
| Subject Discharge from CRU | | | | | | | | | | X | | | | |
| Outpatient Visit | X | | | | | | | | | | X | X | | |
| Investigational Product Administration | | | X | | | | | | | | | | | There is a minimum of 28 days washout period between doses for Period 1 and Period 2. |
| Medical History | X | | | | | | | | | | | | | |
| Height | X | | | | | | | | | | | | | |
| Weight | X | X | | | | | | | | | X | X | | |
| Vital Signs (supine) (hours) | X | X | Predose | 24 | 48 | | | | | | | X | | Time points may be added for each study period, if warranted and agreed upon between Lilly and the investigator. |
| Clinical Laboratory Tests | X | X | | | | | | | | | X | X | | See Appendix 2 , Clinical Laboratory Tests, for details. |
| Adverse Event | X | X | X | X | X | X | X | X | X | X | X | X | X | |
| Injection Site Reaction Assessment (hours) | | | Predose, 0, 6, 12 | 24 | | X | | | | | X | X | X | 0-hour assessment should be performed within 5 minutes after subcutaneous injection. Additional assessments may be performed if deemed necessary by the investigator. |
| PK Samples (hours) | | | Predose | 24 | 48 | 72 | 96 | 120 | 144 | 168 | 336 | X | | Sampling times are relative to the time of study treatment administration (0 hour). Sampling times are given as targets to be achieved within reasonable limits. If a subject withdraws from the study prior to completion of scheduled PK sampling for a given period, every effort will be taken to draw an unscheduled blood sample for PK assessment. This will not be required if a sample has already been taken within the previous 24 hours. For ET, a PK sample can be taken at any time during the visit timed close to the immunogenicity sample. |

| Procedure | Screening | Periods 1 and 2 | | | | | | | | | | ET/Follow-up | Comments |
|------------------------|----------------|-----------------|---------|-------|-------|-------|-------|-------|-------|-------|--------|--|--|
| | Days -28 to -2 | Day -1 | Day 1 | Day 2 | Day 3 | Day 4 | Day 5 | Day 6 | Day 7 | Day 8 | Day 15 | 28 ±3 days after last dulaglutide dose | |
| Pregnancy Test | X | X | | | | | | | | | | X | Females only. Serum pregnancy test will be performed at screening. Urine pregnancy test will be performed for women of childbearing potential at Day -1 for each period and at ET/Follow-up. |
| Physical Exam | X | X | | | | | | | | | | X | After screening, medical assessment only performed to include medical review and targeted examination, as appropriate. |
| 12-lead ECG | X | | | | | | | | | | | X | Single 12-lead ECG will be collected. ECGs must be recorded before collecting any blood samples. Subjects must be supine for at least 5 minutes before ECG collection and remain supine but awake during ECG collection. |
| Genetic Sample | | | X | | | | | | | | | | Single sample for pharmacogenetic analysis taken prior to dosing on Day 1 in Period 1 only. |
| Immunogenicity Samples | | | Predose | | | | | | | | | X | All samples for immunogenicity should be taken predose, when applicable and possible. |

Abbreviations: CRU = clinical research unit; ECG = electrocardiogram; ET = early termination; PK = pharmacokinetic(s).

Note: If multiple procedures take place at the same time point, the following order of the procedures should be used: ECG, vital signs, and venipuncture.

3. Introduction

3.1. Study Rationale

Presently there is an ongoing Phase 2 study (Protocol H9X-MC-GBGJ / Double-Blind, Placebo-Controlled, 18-Week Trial of Investigational Dulaglutide Doses versus Placebo in Patients with Type 2 Diabetes on Metformin Monotherapy) designed to provide initial safety and efficacy data for 2 investigational dulaglutide doses (3.0 mg and 4.5 mg) that are higher than the currently approved 0.75- and 1.5-mg doses; these higher doses could provide data that show improved clinical benefits, including greater reduction in hemoglobin A1c (HbA1c) and greater body weight reduction, with an acceptable safety profile. Prefilled syringes (PFSs) are being used to administer dulaglutide doses in this Phase 2 study.

To confirm applicability of the GBGJ safety and efficacy data to future Phase 3 studies where a single dose pen (SDP) and new formulation (Table GBGM.2) will be used, Study GBGM will evaluate the relative bioavailability of a 4.5-mg dulaglutide dose administered subcutaneously (SC) as a single SDP injection of the new higher dulaglutide concentration (test) compared to the same dose administered as three 1.5-mg PFS injections of the current commercial formulation (reference). Details regarding the new formulation are presented in Module 3 of the CTA.

3.2. Background

Dulaglutide exhibits glucagon-like peptide-1 (GLP-1) mediated effects, including glucose-dependent potentiation of insulin secretion, inhibition of glucagon secretion, delay of gastric emptying, and weight loss. Preclinical and clinical experience to date support the use of dulaglutide as a once-weekly injection to improve glycemic control in patients with type 2 diabetes (T2D).

Dulaglutide received regulatory approval for the treatment of T2D in the United States on 18 September 2014, and in the European Union on 21 November 2014 for use as 0.75- and 1.5-mg doses administered by SDP or PFS (Trulicity® United States Prescribing Information [USPI] 2017; Trulicity® Summary of Product Characteristics [SmPC] 2016).

3.3. Benefit/Risk Assessment

The proposed dose of dulaglutide to be used in this study is 4.5 mg.

Dulaglutide is currently approved for use as 0.75- and 1.5-mg doses. A higher dulaglutide dose of 4.5 mg in healthy subjects was chosen for this study (GBGM) based on simulations which included data collected in Studies GBCD and GBCF (Barrington et al. 2011, Skrivanek et al. 2014).

Study GBCD was a multiple ascending dose study where dulaglutide doses up to 8 mg were administered weekly for 5 weeks to patients with T2D. GLP-1-related gastrointestinal effects (nausea, vomiting, and diarrhea) were of mild to moderate in intensity over the dose range of 1 to 8 mg; therefore, the 8-mg dose was considered to be a tolerable dose. Robust glucodynamic activity consistent with sustained GLP-1 pharmacology was observed over the dose range 0.3 to 8 mg dulaglutide. Reductions in fasting and postprandial glucose, and glucose-dependent insulin

secretion were demonstrated after 5 weeks of once-weekly SC dulaglutide administration. Study GBCF was a Phase 2/3 study in patients with T2D in which dulaglutide doses up to 3 mg were administered weekly, with a limited number of patients at the highest dose of 3 mg. The benefit/risk profile favored the 1.5-mg dulaglutide dose for further development based on a predefined clinical utility index.

The results of simulations including data from Studies GBGD and GBCF suggest the 4.5-mg dose may provide a clinically relevant improvement in Hb1Ac and body weight reduction in comparison to the 1.5-mg dose after 26 weeks.

Nonclinical studies and clinical studies in healthy subjects and in patients with T2D support that dulaglutide may be safely administered to humans with careful monitoring for potential adverse effects. Dulaglutide-related changes in both rat and monkey chronic repeat-dose toxicity studies (6 months duration in rats; 9 months duration in monkeys) were generally consistent with, or secondary to, GLP-1 pharmacology. The primary effects of dulaglutide administration to rats and monkeys were dose dependent decreases in food consumption with secondary decreases in body weight gain. None of these effects were adverse to the health of the animals. No dose-limiting target organ toxicity occurred in either species. The no-observed-adverse-effect levels (NOAELs) for target organ toxicity in chronic repeat-dose toxicity studies of dulaglutide in rats (6 months) and monkeys (9 months) were 16.3 mg/kg and 8.15 mg/kg, respectively. Relative to the maximum human dose in Study GBGJ (4.5 mg/week), the predicted area under the concentration versus time curve (AUC) exposure multiples at the NOAELs in rats and monkeys are 55- and 162-fold, respectively. Similar to other GLP-1R agonists, fetal skeletal effects were observed in the embryo-fetal development studies of dulaglutide in pregnant rats and rabbits. The fetal skeletal effects occurred at 15- and 4-fold the 4.5-mg/week dulaglutide dose in pregnant rats and rabbits, respectively, based on AUC.

There is no anticipated therapeutic benefit for the subjects in this study.

More information about the known and expected benefits, risks, serious adverse events (SAEs), and reasonably anticipated adverse events (AEs) of dulaglutide are to be found in the Investigator's Brochure (IB).

In addition, detailed information about the known and expected benefits and risks of dulaglutide may be found in the Trulicity USPI (2017) and SmPC (2016).

4. Objectives and Endpoints

Table GBGM.1 shows the objectives and endpoints of the study.

Table GBGM.1. Objectives and Endpoints

| Objectives | Endpoints |
|--|---|
| Primary To evaluate the relative bioavailability of a single dose of dulaglutide administered subcutaneously (SC) to healthy subjects as a single injection by single dose pen (SDP; test) compared to 3 injections by prefilled syringe (PFS; reference). | Pharmacokinetic parameters AUC and maximum observed drug concentration (C_{max}) for dulaglutide administered by a SDP compared to PFS. |
| Secondary To assess the tolerability of a single dose of dulaglutide administered SC to healthy subjects as a single injection by SDP compared to 3 injections by PFS. | Incidence of treatment-emergent adverse events. |

5. Study Design

5.1. Overall Design

Study GBGM is a Phase 1, single-center, open-label, randomized, 2-period, crossover study in healthy subjects to evaluate the relative bioavailability of 4.5 mg of a new formulation (Table GBGM.2) of dulaglutide administered SC as a single injection by SDP (test) compared to 3 injections by PFS (reference). Treatment sequences and randomization are described in Section 7.2.

Each subject will provide informed consent for study participation and will undergo a screening examination within 27 days prior to enrollment.

In each treatment period, subjects will be admitted to the clinical research unit (CRU) on Day -1. On the morning of Day 1, following an overnight fast of approximately 8 hours, subjects will receive a single SC dose of dulaglutide administered according to their assigned treatment sequence. Blood samples will be collected predose and up to 336 hours postdose to measure dulaglutide concentrations. At a minimum, subjects will remain at the CRU until collection of the 168-hour (Day 8) pharmacokinetic (PK) sample in each period.

There will be a washout period of at least 28 days between doses in Periods 1 and 2. Each subject will be required to return to the CRU for a follow-up visit 28 ± 3 days after the last dulaglutide dose. The total duration for each subject (from screening through the follow-up visit) is approximately 84 days.

Safety and tolerability will be assessed throughout the study by means of vital sign measurement, physical examination, clinical laboratory tests, electrocardiograms (ECGs), and AE recording.

Study governance considerations are described in detail in Appendix 3.

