5.4. Scientific Rationale for Study Design

Conducting this study in healthy subjects mitigates the potential confounding effects of the disease state and concomitant medications in patients.

An open-label design is required, as subjects and staff administering the injections will be able to distinguish between the SDP and PFS, including number of injections. In order to minimize any potential period-effect, a randomized, 2-sequence, crossover design has been selected. Based on the apparent terminal elimination half-life ($t_{1/2}$) of dulaglutide of approximately 5 days

(Trulicity® USPI 2017), a washout period of at least 28 days between doses is considered sufficient not to impact the PK outcome of the second period.

Pharmacokinetic sampling up to 336 hours is sufficient to generate an evaluable PK profile for dulaglutide. A single dose of dulaglutide will be administered in each period, as this is considered sufficient to evaluate the relative bioavailability of dulaglutide administered via the 2 devices (SDP versus PFS).

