Appendix 5. Blood Sampling Summary

This table summarizes the approximate number of venipunctures and blood volumes for all blood sampling (screening, safety laboratories, and bioanalytical assays) during the study.

Protocol H9X-MC-GBGM Sampling Summary

| Purpose | Blood Volume per Sample (mL) | Number of Blood Samples | Total Volume (mL) |
|---|------------------------------|-------------------------|-------------------|
| Screening tests ^a | 8 | 1 | 8 |
| Clinical laboratory tests ^a | 8 | 5 | 40 |
| Pharmacogenetics | 10 | 1 | 10 |
| Pharmacokinetics | 4 | 19 | 76 |
| Immunogenicity | 10 | 3 | 30 |
| Total | | | 164 |
| Total for clinical purposes (rounded up to nearest 10 mL) | | | 170 |

^a Additional samples may be drawn if needed for safety purposes.

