9.3 Pharmacokinetic Assessment

9.3.1 Pharmacokinetic Analysis

Pharmacokinetic parameter estimates will be determined using non-compartmental procedures in validated software program (Phoenix WinNonlin Version 6.4 or later).

Plasma concentrations of dulaglutide will be used to determine the following PK parameters, when possible:

Parameter	Units	Definition
AUC(0-∞)	ng.h/mL	area under the concentration versus time curve from time zero to infinity
AUC(0-168h)	ng.h/mL	area under the concentration versus time curve from time zero to 168 hours post dose
AUC(0-336h)	ng.h/mL	area under the concentration versus time curve from time zero to 336 hours post dose
AUC(0-t _{last})	ng.h/mL	area under the concentration versus time curve from time zero to time t, where t is the last time point with a measurable concentration
%AUC(t _{last} -∞)	%	percentage of AUC(0-∞) extrapolated
C _{max}	ng/mL	maximum observed drug concentration
t _{max}	h	time of maximum observed drug concentration
t _½	h	half-life associated with the terminal rate constant (λ_z) in non-compartmental analysis
CL/F	L/h	apparent total body clearance of drug calculated after extra-vascular administration
V _z /F	L	apparent volume of distribution during the terminal phase after extra-vascular administration
V _{ss} /F	L	apparent volume of distribution at steady state after extra-vascular administration

Additional PK parameters may be calculated, as appropriate. The software and version used for the final analyses will be specified in the clinical study report. Any exceptions or special handling of data will be clearly documented within the final study report.

Formatting of tables, figures and abbreviations will follow the Eli Lilly Global PK/PD/TS Tool: NON-COMPARTMENTAL PHARMACOKINETIC STYLE GUIDE. The version of the tool effective at the time of PK analysis will be followed.

General PK Parameter Rules

- Actual sampling times will be used in the final analyses of individual PK parameters, except for non-bolus pre-dose sampling times which will be set to zero.

- C_{\max} and t_{\max} will be reported from observed values. If C_{\max} occurs at more than one time point, t_{\max} will be assigned to the first occurrence of C_{\max} .

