- AUC parameters will be calculated using a combination of the linear and logarithmic trapezoidal methods (linear-log trapezoidal rule). The linear trapezoidal method will be applied up to t_{\max} and then the logarithmic trapezoidal method will be used after t_{\max} . The minimum requirement for the calculation of AUC will be the inclusion of at least three consecutive plasma concentrations above the lower limit of quantification (LLOQ), with at least one of these concentrations following C_{\max} . AUC(0- ∞) values where the percentage of the total area extrapolated is more than 20% will be flagged. Any AUC(0- ∞) value excluded from summary statistics will be noted in the footnote of the summary table.
- Half-life ($t_{1/2}$) will be calculated, when appropriate, based on the apparent terminal log-linear portion of the concentration-time curve. The start of the terminal elimination phase for each subject will be defined by visual inspection and generally will be the first point at which there is no systematic deviation from the log-linear decline in plasma concentrations. Half-life will only be calculated when a reliable estimate for this parameter can be obtained comprising of at least 3 data points. If $t_{1/2}$ is estimated over a time window of less than 2 half-lives, the values will be flagged in the data listings. Any $t_{1/2}$ value excluded from summary statistics will be documented in the footnote of the summary table.
- A uniform weighting scheme will be used in the regression analysis of the terminal log-linear portion of the concentration-time curve.
- The parameters based on observed C_{last} will be reported.

Individual PK Parameter Rules

- Only quantifiable concentrations will be used to calculate PK parameters with the exception of special handling of certain concentrations reported below the lower limit of quantitation (BQL). Plasma concentrations reported as BQL will be set to a value of zero when all of the following conditions are met:
 - The compound is non-endogenous.
 - The samples are from the initial dose period for a subject or from a subsequent dose period following a suitable wash-out period.
 - The time points occur before the first quantifiable concentration.
- All other BQL concentrations that do not meet the above criteria will be set to missing.

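### Does the single PK sample 28 days after the last dose leave the primary AUC(0-∞) ill-defined or unequal between periods?

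*Protocol*

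**What the plan says.** Protocol 5.1 states: "Blood samples will be collected predose and up to 336 hours postdose to measure dulaglutide concentrations". SAP 5 repeats this, and Protocol 5.4 gives the reason: "Pharmacokinetic sampling up to 336 hours is sufficient to generate an evaluable PK profile for dulaglutide".

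The PK row of the Schedule of Activities (Protocol 2) goes one step further and ends "120 | 144 | 168 | 336 | X". The X stands under ET/Follow-up, 28 ±3 days after the last dose. The row's comment says of early termination that "a PK sample can be taken at any time during the visit timed close to the immunogenicity sample". Appendix 5 budgets for the extra draw: "Pharmacokinetics | 4 | 19 | 76".

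SAP 9.3.1 uses actual sampling times, "except for non-bolus pre-dose sampling times which will be set to zero", and takes t_last as the last measurable concentration. It names no upper time limit and does not mention the follow-up sample. It attaches two reliability flags. AUC(0-∞) "values where the percentage of the total area extrapolated is more than 20% will be flagged". A half-life that "is estimated over a time window of less than 2 half-lives, the values will be flagged in the data listings" is the second case. SAP 9.3.2 makes Cmax and AUC(0-∞) primary and AUC(0-168h) and AUC(0-336h) secondary, all in one mixed model with treatment, period and sequence.

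**The concern.** Read literally, the SAP's calculation rules would admit a quantifiable follow-up concentration. It follows the last dose only, so for completers it would lengthen Period 2 and not Period 1. The Period 2 predose sample, at least 672 h after the Period 1 dose, does not restore the balance, because it is set to time zero of Period 2.

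AUC(0-∞), AUC(0-t_last), t½ and CL/F could then rest on about 600 to 744 h in one period and 336 h in the other. Two analysts could obtain different values of a primary parameter from the same plan. The two flags would gather in Period 1 because of when blood was drawn. Had this carried into the SDP/PFS ratio or its interval, the primary result would be affected.

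**Working it through.** **Count of samples (the plan's own figure).** Nine samples per period (predose, 24, 48, 72, 96, 120, 144, 168, 336 h) and one at follow-up: 2 × 9 + 1 = 19; 19 × 4 mL = 76 mL. Both match Appendix 5. The late draw is therefore intended, and it occurs once.

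**Timing.** 25 × 24 = 600 h, 28 × 24 = 672 h, 31 × 24 = 744 h.

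**Area beyond the last sample.** The half-life is 120 h (Protocol 5.4, about 5 days). The documents give no tmax, so 24 to 72 h is assumed. With no absorption phase the share beyond T is 2^(−T/120); at 336 h this is 2^(−2.8) = 14.4%. With one-compartment first-order absorption it is (ka·e^(−ke·T) − ke·e^(−ka·T))/(ka − ke):

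| Last sample | tmax 24 h | 48 h | 72 h |
|---|---|---|---|
| 336 h | 15.0% | 16.2% | 18.2% |
| 600 h | 3.3% | 3.5% | 4.0% |
| 672 h | 2.2% | 2.3% | 2.6% |
| 744 h | 1.4% | 1.5% | 1.7% |

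**Slope window.** Two half-lives are 240 h. A fit ending at 336 h spans (336 − 96)/120 = 2.0 half-lives from 96 h, 1.8 from 120 h and 1.6 from 144 h. One ending at the late sample spans from (600 − 144)/120 = 3.8 to (744 − 96)/120 = 5.4. The contrast in flags is therefore real if the late value is quantifiable and used.

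**Effect on the ratio.** Let τ be the log SDP/PFS effect, π the period effect, and d_S and d_P the shifts that the longer Period 2 window causes in log AUC(0-∞) under SDP and PFS. The expected Period 2 minus Period 1 difference is τ + π + d_S in sequence 1 and −τ + π + d_P in sequence 2. Half the difference between sequences is τ + (d_S − d_P)/2.

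- If d_S = d_P, the shift drops out exactly. A least-squares crossover fit with Period 2 shifts of −3%, +3% and +17% returned a ratio of 1.000, with complete data and with unequal dropout.
- In simulation (tmax 48 h, half-life spread 15%, assay error 5 to 15%, all assumed) adding the late sample multiplied mean AUC(0-∞) by 0.999 to 0.990, a log shift of at most about 0.010 in size. If all of that fell on one treatment, the bias would be 0.010/2 = 0.005, about 0.5%.
- AUC(0-t_last) does rise by about 17%, but no treatment comparison of it is planned.

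**Effect on the interval.** Trial-level simulation with n = 18 and within-subject log SD √ln(1 + 0.21²) = 0.2077, in three settings of assumed variability. Mean log half-width of the 90% CI:

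| Window | Setting 1 | 2 | 3 |
|---|---|---|---|
| Unequal (late sample in Period 2 only) | 0.1218 | 0.1230 | 0.1289 |
| 336 h in both periods | 0.1226 | 0.1245 | 0.1335 |
| Late sample in both periods | 0.1210 | 0.1215 | 0.1233 |

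Across all options the ratio is 1.000 to 1.001 and coverage 0.899 to 0.908. The unequal window is slightly tighter than 336 h in both periods, so using the extra sample does not widen the interval.

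**The case for a change.** The strongest case for acting is that SAP 3 presents its design material as an aid to the reader, so the 336 h statement in SAP 5 is not a calculation rule, and the rules in SAP 9.3.1 would let the late value in. The study is open-label and the choice could be made with data in hand. The SAP also does not say whether a flagged AUC(0-∞) stays in the primary model. With assumed half-life CV 15 to 25% and assay CV 10 to 15%, simulation puts the 20% flag on 20 to 49% of 336 h profiles. If those were dropped from Period 1, 18 complete pairs would become about 18 × 0.80 = 14 to 18 × 0.51 = 9. The log half-width, t × 0.2077 × √(2/n), would grow from 0.121 to 0.140 (n = 14) or 0.186 (n = 9).

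The silence stands as a fact. The loss of pairs does not follow from it. SAP 9.3.1 prescribes a flag, not removal from the model, and requires exclusions from summary statistics to be footnoted. Nor would a common 336 h window help: flags would then arise in both periods, and at least as many pairs would be touched.

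The alternative of equalising at the long end, with the Period 2 predose value as the last Period 1 point, gains little: 0.6 to 4.3% of CI width against unequal windows, and about 0 to 3.4% with an assumed LLOQ of 2 to 5% of Cmax. With that LLOQ both late values would be quantifiable in only 2 to 53% of subjects, so 47 to 98% would fall back to 336 h and the window would depend on the subject's own concentrations.

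**Conclusion.** This is a gap that analysts can fill sensibly, and closing it brings no material gain. Protocol 5.1 and 5.4 and SAP 5 all describe a 336 h profile, and the schedule's remark on early termination pairs the late draw with the immunogenicity sample. The natural reading is a companion to the antibody test, with both periods analysed to 336 h. On the other reading the SDP/PFS ratio stays at about 1.00 and coverage at about 0.90. Cmax, AUC(0-168h) and AUC(0-336h) are essentially untouched, and AUC(0-336h) already gives a same-window comparison in the same model. The choice would also be visible, since the SAP reports the percentage extrapolated, marks terminal points on the plots and requires special handling of data to be documented.

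What is left is descriptive: by-treatment summaries of t½ and AUC(0-t_last) might mix two windows, about equally for the two treatments because the sequences are balanced.

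The ratio result needs the period term and a similar window effect under both treatments. The sizes rest on the stated 120 h half-life and on assumed tmax, variability and LLOQ. Whether the late sample is quantifiable at all cannot be settled from the documents: the expected concentration at 672 h is 2.5 to 4.0% of Cmax, and no LLOQ is given.
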